2.0 Abbreviations

AE	Adverse Event
5-ASA	5-Aminosalicylic Acid
CDAI	Crohn's Disease Activity Index
CRA	Clinical Research Associate
CRF	Case Report Form
CD	Crohn's Disease
SAE	Serious Adverse Event
MFDS	Ministry of Food and Drug Safety
PCDAI	Pediatric Crohn's Disease Activity Index
PMS	Post-Marketing Surveillance
PPD test	Purified Protein Derivative test
TB	Tuberculosis
TNF	Tumor Necrosis Factor

4.0 Abstract

Title: Post-Marketing Surveillance of Humira® in Korean Pediatric CD Patients under the “New-Drug Re-examination”
Rationale and Background: This non-interventional, observational study will be conducted in compliance with the New Drug Re-examination Guideline in Korea
Research Question and Objectives: To evaluate the safety profile of Humira® for Pediatric CD patients in normal medical practice: (1) Serious adverse event•adverse drug reaction (2) Unexpected adverse event•adverse drug reaction (3) Already known adverse drug reaction (4) Non-serious adverse drug reaction (5) Adverse events resulting from drug misuse, drug abuse or drug interaction (6) Other information related to the product’s safety and effectiveness (including the influence to the laboratory value)
Study Design: Post-Marketing Surveillance
Population: Pediatric CD patients who have been prescribed Humira® by the treating physician
Variables: Demographics, Medical History, PPD Skin Test, Chest X-ray, Interferon Gamma Release Assay, Concomitant Medication, Safety, PCDAI score (CDAI score if it is evaluated)
Data Sources: paper Case Report Form
Study Size: 141 patients
Study Duration : 12 Sep 2013 ~ 11 Sep 2017
Data Analysis: (1) The safety analysis data set : all subjects who have received at least one dose of Humira® during the study and have been followed up for the safety information (2) The effectiveness analysis data set: 
Effectiveness of Humira® induction therapy: all subjects who have been administered Humira® and received Humira® for 4 weeks including induction period (± 1 week) and for whom effectiveness evaluation parameters have been recorded.Maintenance effectiveness of Humira®: all subjects who have been administered Humira® and received Humira® for 6 months (± 4 weeks) and for whom effectiveness evaluation parameters have been recorded.
Milestones: (1) Start of Data collection : 1Q 2015 (2) End of Data collection : 3Q 2017 (3) Final Report of Study Results : 4Q 2017

5.0 Amendments and Updates

The purpose of the amendments and updates is below:

11.1.6 Pregnancy Reporting	To clarify a scope of expedited reporting requirements for pregnancy	Amendment 1
11.1.7 Malignancy Reporting	To add Humira specific expedited reporting requirements for Malignancies in Pediatric and Young Adult Patients according to global SOP	Amendment 1
11.2 Product Complaint	To add a definition of product complaints and reporting requirements	Amendment 1
9.5 Study Size/9.7 Data Analysis	To change the number of subjects to be collected for surveillance to meet the local regulatory requirements	Amendment 2

In addition, administrative changes were incorporated to clarify the person in charge and the references.

6.0 Milestones

Major study milestones and their planned dates are as follows:

Start of Data Collection: 1Q 2015

End of Data Collection: 3Q 2017

Final Report of Study Results: 4Q 2017 (Date of submission to MFDS: 11 December 2017)

7.0 Rationale and Background

Rationale

This surveillance will be conducted in compliance with the New Drug Re-examination Guideline in Korea and this protocol is written in accordance with the guideline. Safety data of this study will be compared to product label claim for evaluation of the consistency of the safety profile in the real word setting.

Background

Approximately 25% of IBD patients are diagnosed as children, and the IBD characteristics of pediatric patients differ from those of adults as outlined below.¹⁻³ A recent single center study showed that the incidence of pediatric IBD has been rapidly increasing in Korea in recent years.⁴ In this study, relevant family history was less prevalent and phenotypic expression differed from what was seen in Western countries.

Children with Crohn's disease can experience abdominal pain, intestinal obstruction and strictures, fistulas, abscesses, perianal disease, adverse events of treatment such as corticosteroids and surgery, and nutritional complications. A major difference between adult and pediatric CD is an impact of malnutrition. It can lead to delayed puberty and growth impairment which result in significant psychosocial complications.⁵⁻⁸ At first, the goal of treatment of CD for children is to induce and maintain clinical remission. Restoration and/or preservation of normal growth and pubertal development are additional therapeutic goals in children with CD.⁹

The first line conventional therapy for mild patients includes 5-aminosalicylates and exclusive enteral nutrition (EEN). Corticosteroids are prescribed for moderate patients for induction. Immunomodulators such as azathioprine, 6-MP or MTX are used for maintenance for those.¹⁰

Therapeutic options for Crohn's disease are evolving, and recently, a new treatment approach has been suggested using biological agents to heal mucosa and alter natural history of disease.¹¹⁻¹²

Until now, TNF blockade including adalimumab and infliximab has been prescribed for adult CD patients. In randomized controlled trials, adalimumab rapidly induced and

maintained clinical remission in adults.¹³⁻¹⁷ The efficacy and safety of adalimumab for induction and maintenance of clinical remission in Western children with moderate to severe CD who had failed corticosteroids or immunosuppressants, including prior infliximab in > 40% of subjects, was demonstrated in the Imagine 1 trial.

This study will evaluate the safety and effectiveness of adalimumab for Korean pediatric patients with moderate to severe Crohn's disease (CD).

8.0 Research Question and Objectives

The objective of this surveillance is to evaluate the following items regarding the safety profile of Humira® for Pediatric CD patients in normal medical practice:

- (1) Serious adverse event & adverse drug reaction
- (2) Unexpected adverse event & adverse drug reaction
- (3) Already known adverse drug reaction
- (4) Non-serious adverse drug reaction
- (5) Adverse events profile resulting from drug misuse, drug abuse or drug interaction
- (6) Other information related to the product's safety and effectiveness (including the influence to the laboratory value)

The hypothesis of this study is that Humira® will present a safety profile consistent with that seen in the phase 3 clinical studies and will be efficacious in Korean Pediatric CD patients.

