9.0 Research Methods

9.1 Study Design

This study is a non-interventional, observational study of Humira® in the treatment of pediatric CD as per the New Drug Re-examination Guideline in Korea.

This study will be conducted in institutions which provide a written agreement to AbbVie Korea, and where the use of Humira® for pediatric CD is following their normal medical practice setting. Pediatric patients who are prescribed Humira® as per physician's medical judgment in accordance with the approved SmPC will be enrolled in the study.

As this is a post marketing surveillance, AbbVie is NOT involved in the product supply since the drug is being used according to the approved marketing label and is to be prescribed by the physician under usual and customary practice of physician prescription.

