The effectiveness assessment of Humira® induction therapy and maintenance therapy will be presented by the number and percentage of the subjects with clinical response. Clinical response is defined as decrease in PCDAI score from baseline by ≥ 15 points and if CDAI score is collected, Clinical response is defined as decrease in CDAI score from baseline by ≥ 70 points.

To investigate the factors affecting the effectiveness, the number and percentage of subjects with clinical response will also be classified by background factors (e.g., demographic factors, treatment factors such as medical history, dosing and administration, concomitant medications, beginning of administration before/after the registration date, etc.) and tabulated. If the effectiveness evaluation of above factors has statistical significance, it will be presented as a separate item.

Statistical Methods

The descriptive statistics for safety and effectiveness parameter in each year will be presented in annual reports.

In final report (Re-examination report), safety and effectiveness outcome by background factor will be summarized and analyzed. The analysis for categorical variables will be performed using chi-square test or fisher's exact test and continuous variables will be performed using Wilcoxon rank sum test or t-test. Also, incidence rate of adverse event collected in overall PMS period will be analyzed and 95% CI will be presented.

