9.9 Limitations of the Research Methods

Open-label data from non-randomized patients; reporting bias with historical safety data.

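### Section 8.0 hypothesises that Humira will be efficacious, but one uncontrolled cohort reported as a bare response percentage can neither confirm nor refute that

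*Combined protocol and SAP*

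**What the plan says.** Section 8.0 puts forward a two-part hypothesis. The safety part names what it is to be judged against: "Humira® will present a safety profile consistent with that seen in the phase 3 clinical studies". Section 7.0 adds a second yardstick: "Safety data of this study will be compared to product label claim for evaluation of the consistency of the safety profile". The effectiveness part says only that Humira "will be efficacious in Korean Pediatric CD patients".

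Section 9.1 describes the design: "This study is a non-interventional, observational study of Humira® in the treatment of pediatric CD". There is one cohort and no control group.

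On analysis, Section 9.7 says: "The effectiveness assessment of Humira® induction therapy and maintenance therapy will be presented by the number and percentage of the subjects with clinical response". The responder rule is a within-patient change: "Clinical response is defined as decrease in PCDAI score from baseline by ≥ 15 points", or a CDAI fall of at least 70 where CDAI is collected. The same section leaves out of the effectiveness set children with missing scores and those who stopped treatment before the assessment. Its significance tests compare outcomes across background factors. Its 95% CI is specified for adverse event incidence.

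Section 9.9 reads, in full: "Open-label data from non-randomized patients; reporting bias with historical safety data".

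**The concern.** A hypothesis needs some result that would count against it. The safety part has at least a named reference. The effectiveness part has none, and the planned output is a percentage that nothing in the plan says how to interpret. A fall in PCDAI after starting treatment can reflect the drug, other treatment (Section 9.3 records concomitant corticosteroids and immunosuppressants), or fluctuation in a disease treated when active. A single cohort does not separate these.

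What is at stake is the final report. Section 12.0 says that it will contain results and conclusions and go to the MFDS. With an efficacy hypothesis on record and no criterion attached, what counts as efficacious would be settled after the percentage is known.

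**Working it through.** **1. The plan's own figure.** The only probability the plan calculates is the safety sample-size justification in Section 9.7: a 0.5% event rate in 600 subjects gives a Poisson mean of 600 × 0.005 = 3, and 1 − e^(−3) = 0.9502. This reproduces. It concerns detection of an adverse event. The documents give no null rate, target rate, alpha or power for effectiveness, so there is no effectiveness figure to check.

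**2. The two halves of the hypothesis side by side.**

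| Element | Safety | Effectiveness |
|---|---|---|
| Stated reference | Phase 3 studies (8.0), product label (7.0) | None |
| Control group | None | None |
| Test of the overall rate | None | None |
| Test across background factors | Yes (9.7) | Yes (9.7) |
| 95% CI for the overall rate | Yes (9.7) | None |
| Sample-size basis | Yes (9.7) | None |

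The background-factor tests compare treated children with other treated children, so they do not bear on whether the drug works.

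**3. What precision a response percentage would have.** The number of evaluable children is not given. Table 2 in Section 9.5 expects 141 in total, of whom 71 + 31 = 102 start Humira after enrolment. I use both, and 70 as an assumed lower value to allow for exclusions. The exact (Clopper-Pearson) 95% limits for x responders among n are

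- lower: 2.5% quantile of Beta(x, n − x + 1)
- upper: 97.5% quantile of Beta(x + 1, n − x)

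| n | x | 95% CI | Half-width |
|---|---|---|---|
| 141 | 70 | 41.1% to 58.2% | 8.5 points |
| 102 | 51 | 39.9% to 60.1% | 10.1 points |
| 70 | 35 | 37.8% to 62.2% | 12.2 points |

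This interval describes sampling error only. It does not supply the missing comparison.

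**4. Effect of the exclusions.** Suppose 40% of all starters respond, a share d discontinue before the assessment, and all who discontinue are non-responders. The reported percentage is then 0.40 / (1 − d):

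- d = 10%: 0.40 / 0.90 = 44%
- d = 20%: 0.40 / 0.80 = 50%
- d = 30%: 0.40 / 0.70 = 57%

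The 40% and the values of d are assumptions, because the documents give no discontinuation rate. The direction follows from the exclusion rule whenever those who stop respond less often than those who continue.

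**The case against.** The best defence is that this is a regulatory safety surveillance. The objective in Section 8.0 is the safety profile, and effectiveness enters only within item (6), among other information. The abstract omits the hypothesis, the sample size was justified on safety alone, and Section 7.0 rests efficacy on earlier trials of a product now prescribed under its label. Descriptive reporting of response is acceptable in that setting, and Section 9.9 already discloses the open-label, non-randomized data.

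Most of this stands, and it limits the weight of the point. It does not remove the mismatch: Section 8.0 still states efficacy as a hypothesis, and Section 9.9 does not say that the response percentage cannot answer it.

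Two stronger readings are tempting, and the documents support neither.

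- A reader might infer that any response percentage above zero would be declared a success, and so calculate a near-certain false confirmation. No section states such a rule. Section 9.7 says only that the percentage will be presented. The documents also give no PCDAI variability and no response rate without drug effect, so any such probability would rest wholly on assumptions.
- A reader might infer that the pediatric trial cited in Section 7.0 supplies a threshold to exceed. That section gives no rate and cites the trial for remission, whereas Section 9.7 uses response. If the rate were one seen on adalimumab, such a rule would also defeat itself. With an illustrative reference of 50%, the exact lower limit clears it only with 83 or more responders out of 141, or 62 or more out of 102. If Korean children responded exactly as well, that would happen in 2.1% and 1.9% of studies. The exclusions in step 4 could also push a percentage over a threshold without any better response.

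**Conclusion.** The point holds as a mismatch between a stated efficacy hypothesis and a purely descriptive, uncontrolled analysis. The study cannot confirm or refute efficacy, and a conclusion on that hypothesis would be unsupported. This follows from the text of Sections 8.0, 9.1, 9.7 and 9.9 and needs no numerical assumption.

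The size of the problem cannot be put as an error rate, because there is no decision rule. What can be sized is the precision that goes unreported: about plus or minus 8.5 to 10 points near 50% for 141 down to 102 evaluable children, and wider if exclusions leave fewer. The upward pull from exclusions depends on discontinuation rates that the documents do not give. The safety objectives are unaffected, so this is a point to correct in the wording and not a fault in the surveillance as a whole.

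**What to change.** In Section 8.0, replace the efficacy clause of the hypothesis with a descriptive aim: to estimate the percentage of Korean pediatric CD patients with clinical response at week 4 and at 6 months.

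In Section 9.7, under the effectiveness analysis, add two statements:

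1. Each response percentage will be given with an exact (Clopper-Pearson) 95% CI.
2. The percentage comes from an uncontrolled cohort and excludes subjects who discontinued before the assessment or whose scores are missing. It will not be used to conclude efficacy.

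Do not add a threshold taken from the cited pediatric trial, for the reasons given above.

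The cost is a few sentences, made before the data are locked, with no new data and no more patients. The downside for the sponsor is that the final report can no longer state that efficacy was confirmed.

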9.0 Research Methods

9.1 Study Design

This study is a non-interventional, observational study of Humira® in the treatment of pediatric CD as per the New Drug Re-examination Guideline in Korea.

This study will be conducted in institutions which provide a written agreement to AbbVie Korea, and where the use of Humira® for pediatric CD is following their normal medical practice setting. Pediatric patients who are prescribed Humira® as per physician's medical judgment in accordance with the approved SmPC will be enrolled in the study.

As this is a post marketing surveillance, AbbVie is NOT involved in the product supply since the drug is being used according to the approved marketing label and is to be prescribed by the physician under usual and customary practice of physician prescription.

9.2 Setting

Selection of Study Population

Pediatric CD patients who has been prescribed Humira® by the treating physician as per Korean label will be enrolled.

The patients who are receiving Humira® for pediatric CD during study period and meet the inclusion /exclusion criteria will be enrolled in the sites which signed a contract with AbbVie.

Once the study agreement is in place, the surveillance will be initiated at the site, and all patients who are prescribed Humira® for pediatric CD treatment during the surveillance period and who meet the inclusion /exclusion criteria will be enrolled in the study until the assigned number of subjects are registered at the site.

Inclusion Criteria

1. Pediatric patients with Crohn's Disease who are prescribed Humira in accordance with the Korean label for Humira authorization (labeling)
2. Patients who have given written authorization or patients whose legal representatives have given it to use their personal health data for the purposes of this study.

Physician will refer to the product market authorization (label) for inclusion criteria.

Exclusion Criteria

Patient with any of the following should not be registered in this surveillance:

1. Any contraindications to Humira as listed on the approved product market authorization (labeling)
2. Patients who is participating on other clinical trials.

Patients will be observed for 6 months following first dose of Humira®.

It is planned to include all patients who are treated with Humira® until the planned number of cases are collected to obtain meaningful safety data including TB incidence in the early stage of the study conduct. Once this study has been initiated in an institution, physicians are recommended to include/recruit all eligible patients who are prescribed Humira®.

An evaluable patient is a patient who has been administered Humira® at least once and has safety information at subsequent visits. (or telephone contact, correspondence)

Drop-out patients also will be considered for safety evaluation, if the safety information is obtained by follow-up contact. If there is loss of follow-up, the reason will be recorded.

Investigator Selection Criteria

The surveillance will be conducted in medical institutions in Korea. The institutions include clinics and hospitals. The physician must meet the following criteria:

1. A physician who is working in a hospital or clinic and has a patient pool eligible for this surveillance.
2. A physician who can conduct the study in accordance with the protocol.
3. A physician who agrees to devote adequate time to conduct of the study including enrollment activities, following up the patients and filling out the case report forms.
4. A physician who will report to the sponsor any safety and effectiveness data in accordance with the protocol.

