Regardless of results of causality assessment, presence of adverse event(s), type of adverse event(s), onset, end date, severity, causality assessment by physician on the adverse event(s), action taken, outcome will be captured, during the study, from the first administration to the surveillance period (from informed consent to up to 70 days following the last administration of Humira®) (Section 11.0 Management and Reporting of Complaints).

Effectiveness

From the patients treated with Humira®, the effectiveness data (i.e. PCDAI score) at previous times before Humira® treatment, at 4 weeks (visit window: ± 1 week) and at 6 months (visit window: ± 4 weeks) post-treatment will be collected. (CDAI score will be collected as well, if possible.)

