† The mean number of patients: The number of patients prescribed with anti-TNF agents for relevant disease codes (K500, K501, K508 or K509); source: Health Insurance Review & Assessment Service; unit: people

‡ Percent: calculated by dividing the mean number of patients by the number of patients diagnosed

3) Difficulties in getting patients' consents

Pediatric CD is indicated for pediatric patients, it is difficult to get pediatric patients' consents from their parents.

However, we will make every effort to enroll maximum number of subjects. We expect maximum 141 patients will be recruited [Table 2].

[Table 2] The number of subjects expected to be enrolled in this study

Classification	No. of subjects
Enrolled subjects as of October, 2016	100
- subject who start Humira treatment after enroll in the study	71
- subject who starts Humira treatment before enroll in the study	29
Estimated No. of subjects to be enrolled	Approx. 41
- subject who will start Humira treatment after enroll in the study	31*
- subject who starts Humira treatment before enroll in the study	10
Total	Approx. 141

* Calculated as follows: 5.07 (mean number of newly diagnosed patients per month) x 6 months (remaining enrollment period) = 30.42

About 15 investigators across the country will be participating in this surveillance and the number of subjects to be collected by each investigator will vary.

Study Duration

The study duration designated by MFDS is from 12 September 2013 to 11 September 2017. The study will start after the launch of the product as a new drug for pediatric CD and the final report will be submitted to MFDS by 11 Dec 2017. Interim study reports will be submitted to MFDS every 6 months for the first 2 years, then annually thereafter during PMS period.

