9.7 Data Analysis

Justification for the planned sample size

Information on at least 600 subjects will be collected in this surveillance study in accordance with the Korean regulations on New Drug Re-examination (i.e. New Drug Re-examination Standards: Ministry of Food and Safety (MFDS)).

The sample size of 600 has been selected in order to give at least 95% probability of detecting at least one uncommon SAE that occurs in the Korean patient population at a rate of at least 0.5%. This estimate is based on the assumption that the occurrence of AEs has a Poisson distribution and that if the population rate of occurrence of an AE is 0.5% then the expected number of AEs in the proposed sample size of 600 would be 3. The probability of observing 1 or more events with a Poisson parameter of 3 is 0.95 or 95%.

If we have an AE with a population probability of 0.5% then the expected number of events in a sample size of 600 will be 3. Using the Poisson Distribution with a parameter of 3 the probability of getting zero AEs in our sample size of 600 is given by the formula:

$$\Pr\{X = 0\} = \frac{3^0 \times e^{-3}}{0!} = 1 \times 0.0498 = 0.0498$$

The probability, therefore, of having 1 or more AEs in that sample size is $1 - 0.0498 = 0.9502$.

At least 600 subjects were to be collected for surveillance to meet the local regulatory requirements, but number of subjects to be enrolled was adjusted to 141 subjects. (Refer to section 9.5)

Analysis Population

Number of collected and analyzed patient will be presented as following items: Contracted cases, collected number of CRFs, safety-evaluable cases, effectiveness-evaluable cases, number of drop-out cases, Reasons for drop-out

The safety analysis data set will include all subjects who have received at least one administration of Humira® following the initiation of surveillance and have completed follow up for the safety information.

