For induction effectiveness of Humira®, the effectiveness analysis data set will include all subjects who have been administered Humira® and prescribed Humira® for 4 weeks including induction period (± 1 week) and for whom effectiveness evaluation parameters have been recorded. And for maintenance effectiveness of Humira®, effectiveness analysis data set will include all subjects who have been administered Humira® and prescribed Humira® for 6 months (± 4 weeks) and for whom effectiveness evaluation parameters have been recorded. The subjects whose effectiveness evaluation was not properly conducted because their data from evaluation parameters were missing or they discontinued administration prior to the effectiveness evaluation will be excluded from the evaluation.

Safety Analysis

The adverse events will be coded by MedDRA dictionary. The number and percentage of subjects reporting any serious adverse events/adverse drug reactions will be tabulated overall and by MedDRA 17.0 or more recent version, in preferred term. The number and percentage of subjects reporting unexpected (unlabeled) adverse drug reactions will be tabulated in a similar fashion.

To investigate the factors affecting the safety, the number and percentage of subjects reporting adverse events will also be classified by various background factors (e.g., demographic factors, treatment factors such as medical history, dosing and administration, concomitant medications, beginning of administration before/after the registration date, etc.) and tabulated. If the incidence of adverse events in the subjects who began the administration before/after the registration date has statistical significance, it will be presented as a separate item. In addition, if there are patients who have already been

administered Humira® when participating in the surveillance, their adverse events from the first administration of Humira® to the inclusion will be presented in a separate table. If data from special patient groups are collected, they will be extracted and tabulated separately for adverse events/adverse drug reactions.

Effectiveness Analysis

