10.0 Protection of Human Subjects

Patient written authorization form to use and/or disclose personal and/or health data from legal patient or representative must be obtained prior to enrolling the patient and the physician is required to document this authorization.

However, informed consent will not be required because as local pharmaceutical law does not require informed consent for regulatory-required post-marketing surveillance.

Patient confidentiality must be maintained at all times; therefore demographics that could identify the patients will not be collected.

Monitoring for any sites is not required. However internal consistency check for completeness and consistency of data will be done to ensure integrity of the information reported.

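### Week-4 scores of children registered after week 4 are pooled into the induction response rate, with no safeguard against the loss of early failures among them

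*Combined protocol and SAP*

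**What the plan says.** - **Entry.** Section 9.2 reads: "The patients who are receiving Humira® for pediatric CD during study period and meet the inclusion /exclusion criteria will be enrolled". Other sentences there refer to patients who have been, or are, prescribed the drug. No criterion limits time since first dose, and none addresses children who have already stopped. Under Section 10.0, written authorization "must be obtained prior to enrolling the patient".
- **Prior starters.** Section 9.5, Table 2, has two rows labelled "subject who starts Humira treatment before enroll in the study": 29 of the 100 enrolled by October 2016, and 10 of the roughly 41 still expected.
- **Clock.** It runs from treatment, not registration. Section 9.2 says "Patients will be observed for 6 months following first dose of Humira", and Section 9.3 collects the score "at previous times before Humira® treatment, at 4 weeks (visit window: ± 1 week) and at 6 months (visit window: ± 4 weeks") after treatment starts.
- **Induction set.** Section 9.7 takes "all subjects who have been administered Humira® and prescribed Humira® for 4 weeks including induction period (± 1 week") who have recorded effectiveness parameters. Prior starters are not excluded. Children who stop before the evaluation are.
- **Breakdown.** Section 9.7 tabulates response by whether treatment began before or after registration, as one of the factors affecting effectiveness. A significant result becomes a separate item.
- **Safety by contrast.** Section 9.7 puts prior starters' adverse events from before inclusion in their own table. Section 9.9 names bias from historical data for safety only.

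**The concern.** Take a child who has not responded at week 4 and stops at week 8. Registered at first dose, this child counts as a non-responder. At a site that first registers patients when this child would be at week 12, the child has left treatment, and the protocol describes no step that would find and enrol such a patient. A responder at the same site is still attending and can be registered, and the week-4 score is then taken from the record.

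For prior starters registered after week 4, presence in the data can therefore depend on the outcome being measured. The exclusion of children who stop before evaluation does not help, because these children stop after it.

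Two things are at stake. The pooled induction response may be too high. And a before/after difference produced by selection may be reported as a factor that influences effectiveness. The point concerns the response rate, not adverse-event incidence.

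**Working it through.** **Reproducing Table 2.** The projection for new starters is "5.07 (mean number of newly diagnosed patients per month) x 6 months (remaining enrollment period) = 30.42", rounded up to 31.
- New starters: 71 + 31 = 102.
- Prior starters: 29 + 10 = 39.
- Total: 102 + 39 = 141, as stated. Prior starters are 39/141 = 27.7%.

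**Assumed inputs.** The documents give no expected response or stopping rate and no distribution of registration times. Let:
- r = true week-4 response, 60-70%;
- s = share of starters who stop after week 4 but before they could be registered, 10-30%;
- q = week-4 response among those who stop, 10-30%;
- k = number of prior starters registered after week 4 with usable scores, 0 to 39.

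All 141 are taken as evaluable, and the other 39 − k prior starters as free of this selection.

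**Formulas.** Response among those left to be registered: c = (r − s·q)/(1 − s). Bias in the pooled rate: (k/141)·(c − r).

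**Worked example** (r = 70%, s = 20%, q = 10%, k = 39): c = (0.70 − 0.02)/0.80 = 85%. Pooled = (102 × 0.70 + 39 × 0.85)/141 = 104.55/141 = 74.1%, a bias of +4.1 points.

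| r | s | q | c | Bias, k = 39 | k = 20 | k = 10 |
|---|---|---|---|---|---|---|
| 60% | 10% | 30% | 63.3% | 0.9 | 0.5 | 0.2 |
| 60% | 30% | 10% | 81.4% | 5.9 | 3.0 | 1.5 |
| 70% | 10% | 30% | 74.4% | 1.2 | 0.6 | 0.3 |
| 70% | 20% | 10% | 85.0% | 4.1 | 2.1 | 1.1 |
| 70% | 30% | 10% | 95.7% | 7.1 | 3.6 | 1.8 |

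Bias is in percentage points. It is 0 when k = 0, and also when q = r, that is, when stopping is unrelated to response.

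**Cross-check with another model.** Let rel be the chance that a non-responder is still there to be registered, relative to a responder. Prior starters then show r/(r + (1 − r)·rel). At r = 60% and rel = 0.5 this is 0.60/0.80 = 75%, and the pooled rate with k = 39 is 64.1% (+4.1 points). At r = 70% and rel = 0.5 the bias is +3.4 points. With rel = 1 it is 0. At the limit where no non-responder is ever registered late, it is 8.3 points (r = 70%) to 11.1 points (r = 60%).

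**Would the planned comparison reveal it?** For 102 against 39 at two-sided 0.05, power is about 44% in the worked example (70% against 85%). At rel = 0.5 it is 38% (r = 60%) and 30% (r = 70%). A non-significant result would not show that the selection is absent.

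**Precision after the change.** Half-width = 1.96 × √(0.7 × 0.3/n): 7.6 points at n = 141 and 8.9 points at n = 102.

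**The case against.** The strongest reply is that the text never makes current use at registration a condition. A reader might infer from Section 9.2 that a child is admitted only while still on drug, and that one who stopped at week 8 can never enter. The documents do not support that. The sentence refers to receiving the drug during the study period, which runs from 12 September 2013 to 11 September 2017, and other sentences speak of having been prescribed it. The safety set asks only for "all subjects who have received at least one administration of Humira® following the initiation of surveillance". A child who started and stopped after the site opened could be read as eligible. This stands: the wording does not bar stoppers. What remains is that no procedure captures them.

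The direction and size are also inputs, not results. Only prior starters registered after week 4 with both scores recorded can contribute, and their number is unknown. The top of the range needs 0.3 × 0.9/0.3 = 90% of non-responders to stop before registration. This stands too, so the range has to start near 0.

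Response is already tabulated by start before or after registration whatever the p-value, so the new-starter rate will be visible. That is a partial remedy. It does not change the pooled rate, and it presents the split as a factor affecting effectiveness.

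Finally, safety is the main objective, and no response target exists for a bias to overturn. Even 7 points is within the 7.6-point half-width. That limits the consequences. But Section 8.0 lists effectiveness under its objectives and includes efficacy in its hypothesis, so the rate will be reported and read.

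**Conclusion.** The concern holds as a design weakness with a conditional bias. The plan admits about 39 of 141 subjects who started before registration, without limit on time since first dose, and pools their week-4 scores with those of new starters. It separates pre-inclusion events for safety but does nothing equivalent for response.

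If week-4 non-responders stop sooner than responders, pooled induction response is too high. Under the stated assumptions the excess runs from near 0, when few of the 39 registered after week 4 or stopping is unrelated to response, to about 7 points when all 39 did. More extreme retention assumptions would give more.

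A reader might go further and conclude that the reported response is certainly overstated. The documents do not show that: they give no stopping rates, no response rates and no registration times.

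**What to change.** In Section 9.7:
1. Make the main 4-week response rate the one in subjects registered on or before their week-4 assessment: about 102 new starters plus any prior starter registered by then.
2. Report later-registered prior starters, and the pooled rate, as secondary descriptive results whatever the p-value.
3. Keep the before/after-registration comparison, since it is the one planned check on this selection, but interpret it as such and not as a treatment factor.

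In Section 9.9, add this selection to the limitations.

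The cost is wording and some precision. Treatment start dates are collected under Section 9.3, and start before or after registration is already a planned classifier. Section 9.3 does not list the date of each score as an item, so the plan should state which date decides whether a subject was registered by week 4. With all subjects evaluable and 70% response, the 95% half-width goes from about 7.6 to at most about 8.9 points, and less if some prior starters registered by week 4.
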